## 8.5 Study Stopping Rules

The study will be monitored to ensure that the occurrence of a specified set of treatment related serious adverse events (TRSAEs) that occur during the treatment period does not substantially exceed an anticipated rate. The following specified TRSAEs determined to be probably or definitely related to eltrombopag will be considered for early stopping of the study:

1. Death
2. Any Grade IV toxicity excluding readily reversible metabolic or laboratory abnormalities
3. Grade IV thrombosis/embolism
4. Progression to acute myeloid leukemia by WHO criteria (20% or greater bone marrow or peripheral blood blasts), or other marrow morphology changes deemed concerning by the investigators
5. Increase in reticulin fibrosis grade by 3 points above baseline

We anticipate the rate of these specified TRSAEs within the 16 to 20 weeks study period to be 20% or less. Following Geller et al. (Advances in Clinical Trial Biostatistics, 2004), our stopping rule is determined by a Bayesian approach. The stopping boundary for an experiment is reached if the Bayesian posterior probability that the true probability of developing one or more of the specified TRSAE's exceeds this benchmark rate of 20% is at least 90%. We take our prior distribution to be a beta distribution with parameters  $(\alpha, \beta) = (0.6, 2.4)$ . The parameter are chosen so that the mean  $\alpha / (\alpha + \beta) = 0.2$  as the expected proportion of specified TRSAE's and the sum  $\alpha + \beta = 3$  as the "worth" we place on our prior clinical opinion. This indicates that the relative weight we place on our prior opinion is  $3/30=10\%$  of the weight we will place on the results of the new study. Hence when we make decisions about stopping the study, the data from this study will dominate over the prior opinion. Since we have seen in the past that the first few subjects to be accrued are possibly sicker than the rest of the subjects in the sample, we will start safety monitoring when 3 or more subjects have developed a TRSAE. The following table summarizes the threshold numbers for stopping the study.

Number of subjects in the experiment	Stop if the number of subjects who have developed any of the specified TRSAE's reaches:
$\leq 6$	3
$\leq 9$	4
$\leq 13$	5
$\leq 17$	6

Number of subjects in the experiment	Stop if the number of subjects who have developed any of the specified TRSAE's reaches:
≤ 21	7
≤ 25	8

We investigated the performance of the above stopping rule by a simulation study. In each simulation run, we generated a study with 25 independent Bernoulli trials, each had a probability  $p$  for having TRSAE and  $q=1-p$  for not having TRSAE and compared the TRSAE outcomes with the above stopping boundary to determine whether the study was stopped. We repeated the simulation 100,000 times and computed the proportion of stopped studies (i.e. "number of stopped studies"/100,000) which were stopped using the above stopping rule. The following table summarizes the proportions of stopped studies under a number of scenarios for  $p$ :

Probability of TRSAE = $p$	0.10	0.20	0.25	0.30	0.40
Proportion of Stopped Studies	2.4%	22.7%	41.5%	61.5%	89.7%
Average number of subjects	24.6	21.8	19.3	16.4	11.0
Average number TRSAEs	2.5	4.4	4.8	4.9	4.4

These results suggest that our stopping rule has a low probability stopping a study when the proportion of specified TRSAE is below the benchmark value of 20%, and the probability of stopping a study is high when the true proportion of TRSAE exceeds this benchmark value. Based on these results, we believe that our Bayesian stopping rule has satisfactory statistical properties.

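### Section 8.5 does not say how subjects still under observation count in the safety boundary, and its stated properties assume that every outcome is already known

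*Combined protocol and SAP*

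**What the plan says.** Section 8.5 monitors a list of treatment-related serious adverse events (TRSAEs). The benchmark is tied to a follow-up window: "We anticipate the rate of these specified TRSAEs within the 16 to 20 weeks study period to be 20% or less". The boundary is reached when the posterior probability that the true rate "exceeds this benchmark rate of 20% is at least 90" percent, under a Beta(0.6, 2.4) prior, and "we will start safety monitoring when 3 or more subjects have developed a TRSAE".

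The boundary is printed as a two-column table. The left column is headed "Number of subjects in the experiment". The right column reads "Stop if the number of subjects who have developed any of the specified TRSAE's reaches": 3 for up to 6 subjects, 4 for up to 9, 5 for up to 13, 6 for up to 17, 7 for up to 21 and 8 for up to 25. Nothing in the section says whether a subject joins the left-hand count at enrolment, at first dose or at the end of the window.

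The properties come from a simulation of "25 independent Bernoulli trials, each had a probability" p of a TRSAE. It "compared the TRSAE outcomes with the above stopping boundary to determine whether the study was stopped". No accrual rate, event time or partial follow-up enters. Section 8.3 halts accrual after subject 15 until all 15 reach week 16 to 20. No such wait applies within subjects 1–15 or 16–25.

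**The concern.** Events become known during follow-up, while other subjects are still joining. A subject enrolled yesterday can add to the left-hand count but has had almost no chance to add to the right-hand count. On a plain reading of the column heading as subjects enrolled, such a subject is treated as a completed, event-free case. Three events among the first 6 subjects reach the limit if only 6 are enrolled. They do not if 9 are enrolled when the third event occurs, because the limit is then 4.

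The protocol judges the rule satisfactory from a table in which this cannot happen. If the rule is run on the enrolled count, it stops less often and later than stated, and more subjects are exposed to a drug whose event rate is above the benchmark. Even with a better count, the row for average number of subjects cannot hold once follow-up periods overlap.

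**Working it through.** **Inputs from the documents.** Prior Beta(0.6, 2.4), benchmark 0.20, threshold 0.90, the printed limits, a 16 to 20 week window (8.5); 15 + 10 subjects with a pause between (8.3).

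**Assumptions.** Accrual of one subject per 2 to 13 weeks. The documents give no rate for this trial; the figure of about 35 MDS patients a year in Section 10.1 concerns screening across protocols. Window 20 weeks, constant hazard within it, random (Poisson) arrivals. Like the protocol's simulation, this check ignores a stop for futility at stage 1.

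**Step 1: the stated table.** I ran an exact recursion over 25 subjects, each outcome known before the next enters, with the printed limit L(n) checked after each subject.

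| p | 0.10 | 0.20 | 0.25 | 0.30 | 0.40 |
|---|---|---|---|---|---|
| P(stop), stated | 2.4% | 22.7% | 41.5% | 61.5% | 89.7% |
| P(stop), exact | 2.4% | 22.5% | 41.4% | 61.5% | 89.7% |
| Mean subjects, stated | 24.6 | 21.8 | 19.3 | 16.4 | 11.0 |
| Mean subjects, exact | 24.6 | 21.8 | 19.3 | 16.4 | 11.0 |

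The stated table therefore belongs to immediate outcomes.

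**Step 2: the mechanism.** With s events among n subjects the posterior is Beta(0.6 + s, 2.4 + n − s), so every subject counted without an event adds a full unit to the second parameter. For s = 3, Pr(p > 0.20) is 0.901 at n = 6, 0.764 at n = 9, 0.712 at n = 10 and 0.453 at n = 15.

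**Step 3: boundary read against subjects enrolled.** Simulation, 40,000 runs per cell, limit checked at each event with n = number enrolled at that time.

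| One subject per | P(stop) at 0.20 | 0.25 | 0.30 | 0.40 | Mean enrolled at 0.30 | 0.40 |
|---|---|---|---|---|---|---|
| 2 weeks | 14.4% | 31.4% | 52.9% | 86.5% | 21.0 | 16.8 |
| 4 weeks | 16.2% | 34.4% | 55.6% | 87.3% | 19.4 | 14.5 |
| 8 weeks | 19.3% | 37.5% | 58.5% | 88.6% | 18.0 | 12.8 |
| 13 weeks | 20.0% | 38.8% | 59.4% | 88.8% | 17.4 | 12.1 |
| Stated | 22.7% | 41.5% | 61.5% | 89.7% | 16.4 | 11.0 |

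With event times uniform over the window the results are similar: at p = 0.30, 52.4%, 55.6% and 57.6% for one subject per 2, 4 and 8 weeks.

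In the limit of fast accrual and late events, the boundary acts only at n = 15 and n = 25, and exactly

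P(stop) = P(X₁₅ ≥ 6) + Σₓ₌₀⁵ P(X₁₅ = x) · P(X₁₀ ≥ 8 − x),

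where X₁₅ and X₁₀ are binomial counts. This gives 12.7%, 29.8%, 51.2% and 85.7% at p = 0.20, 0.25, 0.30 and 0.40.

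**Step 4: boundary applied in enrolment order.** Stop as soon as, for any m, the events among the first m enrolled reach L(m). A subject still under observation contributes no event yet, and the counts can only rise. Once all outcomes are in, the rule has stopped exactly when some m has its count at or above L(m). That is the event in Step 1, so the stopping probability does not depend on accrual or event timing. The same simulations give 61.5–61.7% at p = 0.30 and 89.6–89.8% at p = 0.40.

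Only mean enrolment changes:

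| One subject per | Mean at 0.30 | Excess of Step 3 | Mean at 0.40 | Excess of Step 3 |
|---|---|---|---|---|
| 2 weeks | 19.0 | 21.0 − 19.0 = 2.0 | 14.8 | 16.8 − 14.8 = 2.0 |
| 13 weeks | 16.8 | 17.4 − 16.8 = 0.6 | 11.6 | 12.1 − 11.6 = 0.5 |

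The excess is the part due to the denominator. The rest of the rise over 16.4 and 11.0 comes from staggered entry.

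**Step 5: the other obvious reading.** Counting subjects with an event at once, and event-free subjects only when they complete, stops too often. With events spread over the window, P(stop) at p = 0.20 is about 26–42%, because events are known sooner than non-events.

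**The case against.** The strongest reply is that the protocol never says enrolled. A reader might infer that the written rule expressly treats new subjects as event-free, and so that the stated stopping probabilities are wrong. The documents do not support that: the count is undefined, and applied in enrolment order the stated probabilities are right. This stands, and it makes the point one of an undefined count rather than a wrong table. The average-subjects row is the exception, being too low on either reading once follow-up overlaps.

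A reader might also attribute the whole rise in average enrolment to the denominator. Step 4 shows that most of it comes from staggered entry, which no wording removes.

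Three further replies have weight:

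- **Accrual may be slow.** At one subject per 13 weeks the loss at p = 0.30 is about 2 points. The pause after subject 15 also limits the problem, and is included above.
- **The enrolled count has a benefit.** It lowers false stopping, to about 14–20% at p = 0.20 and about 0.6–2.0% at p = 0.10 (stated 2.4%).
- **There are other safeguards.** These are DSMB review every 6 to 12 months (9.1), forwarding of unexpected related SAEs to the DSMB within 7 or 15 days (9.2.4.3), independent review of attribution (9.2.3) and individual discontinuation criteria (8.6). They soften the consequence, but none of them defines the count.

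**Conclusion.** The point holds as an undefined denominator whose plain reading departs from the stated properties. If the count is subjects enrolled, the loss in stopping probability is about 2–9 points at p = 0.30, 3–10 points at p = 0.25 and 1–3 points at p = 0.40. False stopping at the benchmark falls by about 3–8 points. Average enrolment is about 17–21 at p = 0.30 and 12–17 at p = 0.40, of which about 0.5–2 subjects are due to the denominator.

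The sizes rest on the assumed accrual of one subject per 2 to 13 weeks, a 20-week window and constant hazard. The gap nearly closes at the slowest rate. Later events would widen it, and Section 6.2 schedules the marrow examination at week 16, so marrow-based TRSAEs would tend to surface late. The direction was the same in every setting tried. It should be corrected, but it does not invalidate the boundary, whose printed limits can stay.

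**What to change.** Add to Section 8.5 that the boundary is applied in enrolment order: the stopping boundary is reached as soon as, for any m, the number of subjects with a specified TRSAE among the first m enrolled reaches the limit for m, re-checked at each new TRSAE. State whether the five subjects accrued before Amendment L (8.4) and any replacement subjects (8.3) belong to that sequence.

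Keep the stopping-probability row. Restate the average number of subjects, and the average number of TRSAEs with it, under a stated accrual rate. For one subject per 2 to 13 weeks, average enrolment would be about 17–19 at p = 0.30 and 12–15 at p = 0.40.

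The cost is a sentence or two, slightly less favourable averages, and false stopping at the stated 22.7% at p = 0.20 instead of the lower level that the enrolled count would give.

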## 8.6 Off Study Criteria

8.6.1 Per Subject choice: Subjects may withdraw from study at their request. The risks of withdrawing will be discussed, as will alternative treatment options. Those subjects who choose to withdraw while taking eltrombopag will be strongly encouraged to continue to have labs monitored until he/she initiates alternative therapy.

8.6.2 Per principal investigator decision: Should any of the following adverse events occur during the 16 to 20 week study period, or in the extension treatment arm in responders, eltrombopag will be discontinued. The subject will be followed until resolution of the event. Labs will be monitored through 30 days off study drug time point or until he/she initiates alternative disease directed therapy at which time the subject's participation on this study will be considered complete and the subject will go off study.

- Intolerance of eltrombopag not resolved by dose reduction
- Life threatening acute hypersensitivity reaction
- Thrombosis/embolism (DVT, PE, stroke or TIA, myocardial infarction) other than central line thrombosis
- Persistent hepatotoxicity as defined in section 5.3.2
- New or worsening morphological abnormalities or cytopenia(s) (see section 5.4.2)
- No treatment response by week 16, (20 weeks at P.I. discretion)
- Any Grade IV toxicity considered related to the study medication excluding readily reversible metabolic or laboratory abnormalities or hematologic toxicities
- Significant progression of disease or a concomitant condition that would make the subject ineligible for further protocol participation

- Pregnancy or unwillingness to use acceptable forms of contraception
- Initiation of non-protocol therapy for MDS
- Non-compliance with protocol
- Lost to follow-up
- Study completion

Once off study (either by per subject choice or per PI decision), subjects will be referred back to his or her referring physician or consented to the NHLBI evaluation and treatment protocol (94-H-0010) for consideration for standard therapy or evaluation for eligibility for another Branch protocol, depending on what is considered to be in the best interest of the subject.

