**Dose Adjustments for Patients Entering with Platelets  $\leq$  30,000/ $\mu$ L or transfusion-dependence:**

Depending on response and/or tolerability, the daily dose may be increased or decreased according to the following rules:

Platelet Count <math>\leq</math> 30,000/<math>\mu</math>L or transfusion-dependent at baseline	Dose Adjustment or Response
<20,000/ $\mu$ L above base line or platelet transfusion requirement has not decreased following at least 2 weeks of eltrombopag	Increase daily dose by 25 mg (25 mg for East Asians) every 2 weeks to 150 mg/day for non East Asians (75mg/day for East Asians).
$\geq$ 20,000/ $\mu$ L above baseline but $\leq$ 200,000/ $\mu$ L following at least 2 weeks of eltrombopag	Keep at current dosage.
>200,000/ $\mu$ L (untransfused) at any time on study	Decrease dosage by 25 mg (25 mg for East Asians) every 2 weeks to lowest dosage that maintains platelet count $\geq$ 20,000/ $\mu$ L above baseline.
>400,000/ $\mu$ L (untransfused) at any time on study	Discontinue eltrombopag for one week, if platelets < 20,000; restart at 50% of current dose.

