### 5.4 Dose delays, modifications or discontinuation for hematologic side effects

**5.4.1 Thrombosis/Embolism:** Subjects who experience a deep venous thrombosis or a pulmonary embolus, a TIA or stroke, or a myocardial infarction at any time while on eltrombopag will discontinue the drug and go off study. Subjects with platelet counts of > 50,000/ $\mu$ L at the time of thrombosis will be treated with enoxaparin or another appropriate anticoagulant as clinically indicated until the platelet count drops below 20,000/ $\mu$ L with discontinuation of eltrombopag. They will be treated for the thrombotic event as otherwise clinically-indicated.

**5.4.2 Peripheral blood smear shows new morphological abnormalities:** The presence of persistent morphologic abnormalities (red cell teardrop forms or nucleated red blood cells; immature white blood cells) or the development of significant worsening of anemia or neutropenia while on study will require discontinuation of eltrombopag and performance of a bone marrow examination to assess for development of abnormal fibrosis or progression to RAEB-2 MDS or AML.

**5.4.3 Thrombocytosis or erythrocytosis.** Patients will have eltrombopag discontinued for one week if platelets increase to >400,000/ $\mu$ L or Hb to > 16 gr/dL, and if counts have fallen below these cutoffs, drug can be restarted at 50% dosage.

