#### **6.4 Off study assessment four weeks and 6 months after last dose of study drug.**

Subjects who go off study drug due for any reason listed in section 8.6 will be monitored according to the following schedule. At a minimum, subjects must be evaluated at the NIH Clinical Center at 1 month (+/- 1 week) and 6 months (+/- 2 weeks) after the last dose of study medication. The following studies will be performed:

- Clinical Assessment (1 and 6 months)
- CBC with differential (1 and 6 months at NIH and weeks 1, 2 and 3 at home doctor or NIH)
- Acute care, mineral and hepatic panels, CK, LDH, total protein and uric acid (1 and 6 months at NIH and weeks 1, 2 and 3 at home doctor or NIH)
- Reticulocyte count (1 and 6 months at NIH and weeks 1, 2 and 3 at home doctor or NIH)
- Peripheral blood smear (1 and 6 months at NIH and monthly at home doctor if available till seen at NIH)
- Coagulation and thrombosis screens (PT, PTT) (1 month)
- Bone marrow biopsy with reticulin and collagen staining and aspiration with cytogenetics and flow cytometry (flow cytometry at clinician discretion) (6 months)
- Flow cytometry of peripheral blood for GPI (6 months)
- Lymphocyte phenotyping (TBNK flow cytometry, six months +/- 1 week)
- DAT (direct antiglobulin test) at NIH (1 and 6 months, as clinically indicated)
- Type and screen at NIH (1 and 6 months, as clinically indicated)

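### For a DVT related to a central line, section 5.4.1 requires stopping eltrombopag and going off study, while the section 8.6.2 thrombosis criterion can be read as exempting it; nothing says which governs.

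*Combined protocol and SAP*

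**What the plan says.** Section 5.4.1 (Thrombosis/Embolism) names its triggers as "Subjects who experience a deep venous thrombosis or a pulmonary embolus, a TIA or stroke, or a myocardial infarction" and its action as "at any time while on eltrombopag will discontinue the drug and go off study". Line-related events are not excepted. It then sets an anticoagulation rule whose end point assumes the drug has been stopped: "with discontinuation of eltrombopag. They will be treated for the thrombotic event as otherwise clinically-indicated".

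Section 8.6.2 (Off Study Criteria, by principal investigator decision) says eltrombopag will be discontinued if a listed event occurs during the 16- to 20-week period or in the extension, and the subject later goes off study. Its thrombosis entry reads "Thrombosis/embolism (DVT, PE, stroke or TIA, myocardial infarction) other than central line thrombosis". For listed events it adds "The subject will be followed until resolution of the event".

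The next two entries in 8.6.2 point back to their source sections, for example "Persistent hepatotoxicity as defined in section 5.3.2". The thrombosis entry has no such pointer, and 5.4.1 does not refer to 8.6.

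**The concern.** Both sections state what must happen to a subject after a thrombotic event, and both do so in mandatory terms. Section 8.6.2 carves line thrombosis out of a list that itself names DVT, which suggests that some line thromboses would otherwise count as listed events. A DVT associated with a central line then falls under the unconditional stop in 5.4.1 and, on a natural reading, outside the stop in 8.6.2.

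At stake is whether an individual subject stays on a drug whose label, as excerpted in section 10.3.1.2, warns of thrombotic complications at low and normal platelet counts. That should not depend on which section the treating clinician opens. Clarity matters more in extended access, which has no fixed end while the study is open (5.5) and where interim care may be given by home providers (6.3).

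**Working it through.** No arithmetic applies: this is a consistency check of two written rules, and neither depends on a rate, an error level or a sample size.

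**Step 1. Apply both rules to each kind of event.**

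| Event on eltrombopag | 5.4.1 | 8.6.2 thrombosis entry | Conflict? |
|---|---|---|---|
| DVT not related to a line | Stop, off study | Stop, off study | No |
| PE, including one arising from a line clot | Stop, off study | Stop, off study | No |
| Stroke, TIA or myocardial infarction | Stop, off study | Stop, off study | No |
| Clot confined to the catheter, no DVT or PE | Not a named trigger | Exempt | No |
| Line-related DVT | Stop, off study | Exempt, if the undefined term includes DVT | **Yes** |

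Only the last row gives two answers.

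**Step 2. Look for text that resolves it.**

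- Definition: central line thrombosis is mentioned only in the 8.6.2 entry and is not defined there. Nothing says that DVT in 5.4.1 excludes line-related DVT.
- Cross-reference: there is none in either direction. The neighbouring 8.6.2 entries cite 5.3.2 and 5.4.2, and section 5.2 sends non-responders off study by reference to 8.6, so such pointers are used elsewhere.
- Precedence: no statement was found.
- Investigator discretion: 8.6.2 is headed as the principal investigator's decision, but its operative words, like those of 5.4.1, are mandatory. The heading does not clearly settle the question.

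**Step 3. See whether another 8.6.2 entry closes the gap.** A Grade IV toxicity considered related to the drug may be caught by a separate entry, as may a concomitant condition that makes the subject ineligible to continue. A line-related DVT of lower grade, or one not judged drug-related, is not named by any entry. It would come under 8.6.2 only if the investigator applied the concomitant-condition entry.

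**The case against.** The strongest reply is that both sections can be obeyed at once. An event missing from the 8.6.2 list is not permission to continue; 5.4.1 is mandatory, so stopping satisfies both, and stopping is the protective course. This stands, and it limits the point: 8.6.2 does not order continued dosing. What remains is that an express exemption in the off-study criteria invites a clinician to treat the event as not requiring a stop, and nothing there sends that clinician to 5.4.1.

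Safeguards also exist: one main centre, investigator review, adverse event reporting, the count of related Grade IV thrombosis in 8.5, and DSMB review. They limit harm but do not say which rule applies.

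A reader might infer three stronger points that the documents do not support.

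- *Loss of follow-up.* Section 6.4 provides that "Subjects who go off study drug due for any reason listed in section 8.6 will be monitored according to the following schedule", so a subject stopped under 5.4.1 alone might seem to miss the 1- and 6-month assessments. But the concomitant-condition entry can bring that subject under 8.6 and hence 6.4, and adverse event reporting continues after the last dose.
- *That harmonising the wording secures the 6-month visit.* It does not by itself. Section 8.6.2 treats participation as complete once laboratory monitoring reaches 30 days off drug, or alternative therapy begins, even for events it lists.
- *That the anticoagulation end point in 5.4.1 is itself a fault.* It assumes the drug is stopped. If a subject were exempt and stayed on drug, treatment as clinically indicated would remain, which is ordinary care.

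**Conclusion.** The inconsistency is real and narrow. For a line-related DVT, 5.4.1 requires stopping drug and going off study, whereas 8.6.2 can be read as exempting the event, and no text decides between them. The conclusion assumes that central line thrombosis can include a DVT associated with the line. The placement of the exclusion supports that reading, but the protocol does not confirm it.

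This is a minor safety-rule correction that should be made. Its frequency cannot be estimated, because the documents give no rate of central-line use or line-related DVT. A reader might infer an effect on the primary endpoint, since section 8.3 counts subjects who withdraw early for toxicity as non-responders. The documents do not support going that far: the response definition, the two-stage design and the counting rule are the same whichever section governs, and there is no basis for supposing that such events would alter the result.

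**What to change.** The sponsor should choose one rule, state it in identical words in 5.4.1 and 8.6.2, and have each section cite the other.

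- *Default, keeping the mandatory rule in 5.4.1:* limit the 8.6.2 exemption. For example: thrombosis confined to a central line catheter, without DVT or PE, does not by itself require stopping eltrombopag; any line-related DVT or PE does.
- *If line-related DVT is meant to be exempt:* write that exception into 5.4.1, and state there that anticoagulation for a subject who stays on drug is as clinically indicated.

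The documents do not show which the sponsor intended, so the clinical choice is the sponsor's. The cost is protocol wording only, with no change to sample size, visit schedule or analysis.
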